#### Dealing with missing outcome data

The Bayesian linear model will implicitly account for missing outcome data if a patient has at least one of the two NFL levels at 18 or 24 weeks ascertained. If more than 10% of patients in an arm have both NFL levels at 18 and 24 weeks missing, we will use a multivariable Bayesian prediction model that incorporates baseline characteristics, NFL levels pre-randomisation, intermediate NFL levels ascertained at 12 weeks, available NFL levels observed at 18 and 24 weeks and clinical outcomes to derive posterior predictive distributions that allow estimation of pairwise between-group mean differences in NFL levels at 18 to 24 weeks with 95% credible intervals and Bayesian posterior probabilities of non-inferiority or superiority and arm-specific mean changes from baseline with 95% credible intervals and posterior probabilities to reach a reduction from baseline.

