#### Primary outcome analysis

We will use a Bayesian linear model with minimally informative priors that allows for repeated NFL levels assessed at 18 and 24 weeks, with inclusion of baseline NFL levels assessed at the screening visit at -2 weeks and before randomization at week 0. NFL levels originally measured in pg/mL will be log10 transformed to achieve more symmetrical distributions. The primary outcome analysis will follow the intention-to-treat principle, where all patients will be analysed as randomised.

A multivariable Bayesian prediction model that incorporates baseline characteristics and NFL levels pre-randomization and intermediate NFL levels ascertained at 12 weeks as covariates will be used to estimate predictive probabilities of futility and potential effectiveness based on all patients randomised to a trial arm at the time of an interim analysis despite incomplete follow-up. The model can account for all additional data that will accumulate until all patients have completed final follow-up, and appropriately incorporate all sources of uncertainty. Arm-specific Bayesian predictive probabilities for early identification of drugs that are unlikely to be associated with a relevant decrease in NFL levels from baseline will be estimated, declaring futility as described above after at least 16 patients (in case of futility analysis 1) and 20 patients (in case of futility analysis 2) have reached 18 weeks of follow-up. If a trial arm is declared futile, the DMEC will make a recommendation to the TMG who can decide to drop the drug from the trial. A previously dropped candidate drug may re-enter the trial at a higher dose if considered clinically justifiable. The cut-offs used to declare futility, potential effectiveness, non-inferiority or superiority, and decisions on timing and frequency of analyses are based on extensive simulations. A total of 2000 trials were simulated under various scenarios, each trial using 5000 iterations after a burn-in period of 1000 iterations.

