To achieve >80% power for both non-inferiority and superiority analyses, the target sample size is set at 80 patients per candidate drug who will be randomised and followed-up until 18 to 24 weeks. This sample size will result in >80% power to declare non-inferiority to the concurrently randomised reference drug based on a non-inferiority margin of 0.10 log10 units or to declare superiority over the reference drug provided that the true mean reduction in NFL levels associated with the candidate drug is 0.10 log10 units greater than the reduction seen with the reference drug. Non-inferiority will be declared if the Bayesian posterior probability of having a decrease from baseline at 18 to 24 weeks of follow-up that is 0.10 log10 units smaller than the decrease of NFL levels of the reference drug is 2.5% or less. If non-inferiority is reached, we will test for superiority. Superiority will be declared if the posterior probability of having a decrease from baseline larger than the competitor drug is 97.5% or more. To ensure sufficient power of superiority analyses, we will estimate the predictive probability to detect superiority of a candidate drug given the observed data over the reference drug (analogous to conditional power) when 50 randomised patients per arm have reached 18 weeks of follow-up. If the predictive probability is above 60% but below 80%, we will consider increasing the target sample size to reach a predictive probability of 80%. If the predictive probability is below 60% or above 80%, we will adhere to a target sample size of 80 patients per candidate drug. Figure 1 (above) illustrates corresponding analyses and adaptations at trial arm level.

We aim to recruit approximately 700 people with ALS from 11 centres over 43 months and screen between 9 and 20 candidate drugs, depending on the number of drugs that are retained after futility analyses.

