## 12.1 Qualitative sub-study

## Background

Critical to ensuring EXPERTS-ALS is a success, is understanding how trial participants view and experience taking part in an innovative trial design in ALS. Although PPI has informed the trial design, it is important to understand how participants experience the trial, especially if there are modifications we can make to the design or trial processes that improve participation and attrition.

EXPERTS-ALS is innovative in design in a few ways. Firstly, its use of a surrogate marker as an endpoint. Secondly, participation for people with ALS (PwALS) is time-limited and a maximum of 6 months, which is significantly shorter than the usual 2 year involvement in an ALS trial investigating the clinical benefit of treatments. Thirdly, EXPERTS-ALS is an adaptive trial that allows drugs to be identified as futile and immediately dropped from the platform as early as possible. Historically, MND trials have experienced attrition rates, which has been

as high as over 20% (25, 26), and this is associated with a high risk of bias (27). It is unknown how a trial with these innovative design features may affect attrition.

Factors influencing trial participation are also important to understand. Age has been identified as an influencing factor, with older participants being less likely to take part in MND trials (28). However, other social and demographic characteristics are yet to be explored. Understanding potential barriers and enablers to recruitment will ensure the EXPERTS-ALS study processes and procedures can be revised as necessary to be inclusive, and to ensure they do not exclude certain groups so that study findings are generalisable.

As well as understanding pwALS experience of EXPERTS-ALS, the views of multidisciplinary staff implementing platform studies at sites is not well understood. Literature exists which describe the practical considerations for Clinical Trials Unit staff in running platform studies, as well as the resources (29, 30). However, as far as we know, the experience and practical considerations for site staff such as Principal Investigators (PIs)or Research Nurses (RNs) have not been explored. Understanding site staffs' experience of implementing a platform trial will allow us to understand challenges encountered, and if necessary, inform revisions of study procedures and documents for future IMPs in the platform.

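### The 10% missing-data trigger makes the final NFL analysis depend on how much is missing in each arm, and below it week 12 data on patients with no later value go unused

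*Protocol*

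**What the plan says.** Protocol section 11.1, under Dealing with missing outcome data, sets two regimes.

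- Default: "The Bayesian linear model will implicitly account for missing outcome data if a patient has at least one of the two NFL levels at 18" (the second of the two being the week 24 value). Nothing is said there about patients with neither value.
- Switch: "If more than 10% of patients in an arm have both NFL levels at 18 and 24 weeks missing", a multivariable prediction model is used instead. It draws on baseline characteristics, NFL before randomisation, at week 12 and (where available) at weeks 18 and 24, and clinical outcomes. Its purpose is "to derive posterior predictive distributions that allow estimation of pairwise between-group mean differences in NFL levels at 18 to 24 weeks", as well as arm-specific changes and the posterior probabilities.

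Under Primary outcome analysis, the default model "allows for repeated NFL levels assessed at 18 and 24 weeks, with inclusion of baseline NFL levels"; week 12 is not among its listed inputs. The same subsection states: "The primary outcome analysis will follow the intention-to-treat principle, where all patients will be analysed as randomised". For the futility and potential-effectiveness predictions at interim, it uses a model with week 12 NFL as a covariate, "based on all patients randomised to a trial arm at the time of an interim analysis despite incomplete follow-up", with no 10% condition.

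The qualitative sub-study background (section 12.1) reports that attrition in earlier trials in this disease has been "as high as over 20% (25, 26), and this is associated with a high risk of bias". Section 9.10 says withdrawn participants are not replaced.

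**The concern.** Three things do not fit together.

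1. In an arm at or below 10%, a patient with neither late value has no stated route into the final estimate. The stated principle is that everyone is analysed as randomised.
2. The final analysis of such an arm would use less of these patients' data than the interim analysis of the same arm, because their week 12 NFL falls out.
3. Which regime applies is decided by data collected after randomisation, arm by arm. The text does not say what happens to the comparator when only one arm crosses.

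The within-arm change is the most exposed quantity. There is no placebo arm to cancel a bias, and this change decides the first reference drug, through the rule requiring more than 97.5% probability of a reduction after 80 patients reach 24 weeks. Sections 2.1 and 4 give some reason to doubt that missingness is random: higher NFL goes with faster progression and shorter survival, and early rises are linked to more aggressive disease. If patients without late values tend to be those whose NFL was rising, leaving them out makes a drug look better than it is.

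**Working it through.** **Inputs from the protocol.** SD 0.35 log10 units; correlation 0.80 (section 11.2 states it for the futility power; it is assumed here for the final analysis); margin and effect 0.10 log10 units; decision threshold 2.5%. On arm size, "the target sample size is set at 80 patients per candidate drug who will be randomised and followed-up until 18 to 24 weeks".

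**The plan's own figure.** Section 11.2 claims more than 80% power with 80 per arm. For a single change score, SD = 0.35 × √(2 × (1 − 0.80)) = 0.2214, which gives 81.5% power. With baseline adjustment, SD = 0.35 × √(1 − 0.80²) = 0.210, which gives 85.4%. The claim is reproduced.

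**Where the switch falls.** 8/80 = 10.0% does not exceed 10%; 9/80 = 11.25% does. With q = P(9 or more of 80) at the true both-missing rate, and independent arms, P(exactly one of two arms crosses) = 2q(1 − q):

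| True rate, both arms | q | Exactly one arm crosses |
|---|---|---|
| 5% | 0.018 | 0.04 |
| 8% | 0.189 | 0.31 |
| 10% | 0.407 | 0.48 |
| 12% | 0.633 | 0.47 |
| 15% | 0.866 | 0.23 |
| 20% | 0.987 | 0.03 |

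**Bias in an arm mean.** Let d be the amount by which the missing patients' mean change exceeds that of the rest. The protocol gives no value for d, so it is an assumption. Leaving out 10% biases the arm mean by 0.10 × d, in the direction of a larger reduction. With 72 analysed, two standard errors bracket the case:

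- one baseline and one follow-up value: 0.2214/√72 = 0.0261;
- means of two baseline and two follow-up values (equal correlations): SD = 0.35 × √(2 × (0.90 − 0.80)) = 0.1565, and 0.1565/√72 = 0.0184.

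One-sided error = 1 − Φ(1.96 − bias/SE):

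| d (log10) | Bias | SE 0.0261 | SE 0.0184 |
|---|---|---|---|
| 0 | 0 | 2.5% | 2.5% |
| 0.05 | 0.005 | 3.9% | 4.6% |
| 0.10 | 0.010 | 5.7% | 7.8% |
| 0.15 | 0.015 | 8.3% | 12.6% |

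**Simulation of a contrast.** 4,000 trials were simulated with equal true arms of 80, correlation 0.80 between all visits, 8 versus 9 patients missing, and dropout depending on the rise at week 12 (an assumed mechanism of varying strength).

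| Handling | Quantity | Bias (log10) |
|---|---|---|
| Missing patients left out | Within-arm change | −0.010 to −0.019 |
| Left out in both arms | Contrast | 0.000 to −0.002 |
| Left out in one arm, predicted in the other | Contrast | +0.008 to +0.015 |
| Predicted in both arms | Contrast | about 0.000 |

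With missingness completely at random, none of these was biased. The mixed contrast, were it to arise, would be off by up to 15% of the 0.10 margin.

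**The case against.** **Mixing within one contrast is not in the text.** A reader might infer that an arm with 8/80 missing and a comparator with 9/80 must be analysed by two methods in one comparison. The protocol does not say so. The triggered model is described as yielding the pairwise differences, which need both arms, so it may well be meant to cover the whole contrast. This stands. What remains is that the text does not settle it, and that methods could still differ across contrasts and so within the network ranking.

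**Deaths and losses as such are not dropped.** A reader might also infer this. Anyone with a week 18 or week 24 value stays in, and section 9.10 keeps people who stop treatment in follow-up to week 24 if willing. If baseline is modelled as a repeated measure rather than a covariate, baseline-only patients even remain formally in the model. This also stands: only patients with neither value are affected. Either way, they supply no follow-up information and their week 12 value is unused.

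**The interim rules are untouched.** Futility and potential effectiveness are predictive probabilities from a model on all randomised patients. Correct; the point concerns the final analyses only.

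**The assumed gap is large.** A d of 0.10 to 0.15 log10 is a 26 to 41% difference, as big as the trial's own margin and target effect. Section 2.1 describes NFL as mostly stable, with only occasional small rises, and section 4 excludes patients at high immediate risk of death. This is fair, and it is why the table includes d = 0 and 0.05.

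**Discordance matters only near 10%.** True: at 20% missing, nearly every arm would cross.

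**The trigger is prespecified and depends on the amount missing, not on NFL results.** Also true, and it removes any suggestion of choosing a method by its result. It does not explain why available week 12 data should be set aside below the line.

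**Details are deferred to a statistical analysis plan not seen here.** That plan may clarify the comparator question. The 10% rule itself is fixed in the protocol.

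**Conclusion.** The point holds in a limited form. The protocol states a per-arm 10% switch for the final primary analysis and names no method, at or below it, for patients lacking both late values. That they then contribute no follow-up information is the plain reading, though an inference. It fits poorly with the intention-to-treat statement and with the fuller use of week 12 NFL at interim. The within-arm change at 80 patients, with its first-reference-drug rule, is affected most, because no control arm offsets a bias.

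The size is uncertain. If 10% are missing, the one-sided error is about 4 to 5% at d = 0.05 and about 6 to 13% at d = 0.10 to 0.15, against a nominal 2.5%, and is unchanged at d = 0. These figures rest on an assumed d, correlation 0.80 and 72 patients analysed. The protocol's text does not support the broader claims that all deaths and losses are dropped or that a contrast necessarily mixes methods. The change is worth making because it is cheap and removes an avoidable weakness.

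**What to change.** In section 11.1, Dealing with missing outcome data:

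- Delete the 10% trigger.
- Make the prediction model already described there the primary final analysis for every arm and both sides of every contrast, whatever the amount missing.
- Keep the simpler linear model as a sensitivity analysis.
- State how deaths before week 18 enter the analysis.

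**Cost.** The rule is protocol text, so this needs a protocol amendment. Some modelling work follows, because the final model adds clinical outcomes and pairwise estimation to what the interim model has. The simulated operating characteristics may need rechecking. No extra patients or data are needed.

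**Limit.** The prediction model removes bias only so far as observed data, such as week 12 NFL, explain why values are missing.

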#### 11.2 Sample size

In a dataset with repeated NFL levels provided by the Clinical Research in ALS and Related Disorders for Therapeutic Development (CreATe) Consortium, the correlation between repeated measures of log10 transformed NFL levels (pg/mL), obtained within 2 to 8 months, was  $\geq 0.85$  (5). The typical standard deviation at any given measurement time point was 0.35 log10 units.

Figure 1 (above) illustrates the analyses and adaptations at trial arm level. The first futility analysis will be conducted when at least 23 randomised patients per candidate drug reached 12 weeks and at least 16 patients reached 18 weeks of follow-up, which will occur when approximately 28 patients per arm were randomised. This will result in >85% power to detect an average decrease in NFL levels from baseline of 0.15 log10 units and >80% power to declare futility of the candidate drug, assuming a correlation between baseline and follow-up of 0.80. The second futility analysis will be conducted when at least 29 randomised patients per candidate drug reached 12 weeks of follow-up and at least 20 patients reached 18 weeks of follow-up, which will occur when approximately 35 patients per arm were randomised (Figure 1). This will result in >90% power to detect an average decrease in NFL levels from baseline of 0.15 log10 units or declare futility of the candidate drug, assuming a correlation between baseline and follow-up of 0.80. A decrease in NFL levels of 0.15 log10 units, for example, corresponds to a 30% decrease in the geometric mean from 60 pg/mL at baseline to 42 pg/mL at 18 to 24 weeks of follow-up. Of note, since recruitment is accelerating at the beginning of the platform trial, the number of patients randomised will be somewhat higher when futility analyses 1 and 2 will be performed during the first phase of the platform trial.

Potential effectiveness in decreasing NFL levels will be declared if the Bayesian predictive probability of a candidate drug to reach any reduction from baseline at 18 to 24 weeks of follow-up is 97.5% or more. Futility or potential harm will be declared if the posterior predictive probability of a candidate drug to reach a reduction of at least 0.15 log10 units at 18 to 24 weeks of follow-up is 1% or less.

To achieve >80% power for both non-inferiority and superiority analyses, the target sample size is set at 80 patients per candidate drug who will be randomised and followed-up until 18 to 24 weeks. This sample size will result in >80% power to declare non-inferiority to the concurrently randomised reference drug based on a non-inferiority margin of 0.10 log10 units or to declare superiority over the reference drug provided that the true mean reduction in NFL levels associated with the candidate drug is 0.10 log10 units greater than the reduction seen with the reference drug. Non-inferiority will be declared if the Bayesian posterior probability of having a decrease from baseline at 18 to 24 weeks of follow-up that is 0.10 log10 units smaller than the decrease of NFL levels of the reference drug is 2.5% or less. If non-inferiority is reached, we will test for superiority. Superiority will be declared if the posterior probability of having a decrease from baseline larger than the competitor drug is 97.5% or more. To ensure sufficient power of superiority analyses, we will estimate the predictive probability to detect superiority of a candidate drug given the observed data over the reference drug (analogous to conditional power) when 50 randomised patients per arm have reached 18 weeks of follow-up. If the predictive probability is above 60% but below 80%, we will consider increasing the target sample size to reach a predictive probability of 80%. If the predictive probability is below 60% or above 80%, we will adhere to a target sample size of 80 patients per candidate drug. Figure 1 (above) illustrates corresponding analyses and adaptations at trial arm level.

We aim to recruit approximately 700 people with ALS from 11 centres over 43 months and screen between 9 and 20 candidate drugs, depending on the number of drugs that are retained after futility analyses.

## 12. Ancillary sub-studies

Participants will be asked to provide consent to additional future research using their data and/or samples. The appropriate approvals will be obtained prior to any additional research being undertaken.

## 12.1 Qualitative sub-study

## Background

Critical to ensuring EXPERTS-ALS is a success, is understanding how trial participants view and experience taking part in an innovative trial design in ALS. Although PPI has informed the trial design, it is important to understand how participants experience the trial, especially if there are modifications we can make to the design or trial processes that improve participation and attrition.

EXPERTS-ALS is innovative in design in a few ways. Firstly, its use of a surrogate marker as an endpoint. Secondly, participation for people with ALS (PwALS) is time-limited and a maximum of 6 months, which is significantly shorter than the usual 2 year involvement in an ALS trial investigating the clinical benefit of treatments. Thirdly, EXPERTS-ALS is an adaptive trial that allows drugs to be identified as futile and immediately dropped from the platform as early as possible. Historically, MND trials have experienced attrition rates, which has been

as high as over 20% (25, 26), and this is associated with a high risk of bias (27). It is unknown how a trial with these innovative design features may affect attrition.

Factors influencing trial participation are also important to understand. Age has been identified as an influencing factor, with older participants being less likely to take part in MND trials (28). However, other social and demographic characteristics are yet to be explored. Understanding potential barriers and enablers to recruitment will ensure the EXPERTS-ALS study processes and procedures can be revised as necessary to be inclusive, and to ensure they do not exclude certain groups so that study findings are generalisable.

As well as understanding pwALS experience of EXPERTS-ALS, the views of multidisciplinary staff implementing platform studies at sites is not well understood. Literature exists which describe the practical considerations for Clinical Trials Unit staff in running platform studies, as well as the resources (29, 30). However, as far as we know, the experience and practical considerations for site staff such as Principal Investigators (PIs)or Research Nurses (RNs) have not been explored. Understanding site staffs' experience of implementing a platform trial will allow us to understand challenges encountered, and if necessary, inform revisions of study procedures and documents for future IMPs in the platform.

We want to explore how the expectations and experience of participants influence the decision to participate and remain in EXPERTS. We will explore trial participant and decliner decision making for participation in EXPERTS including barriers and enablers to recruitment. We will explore participant experience in the trial, exploring views on design elements such as use of a surrogate marker and time-limited participation, and how key events such as study arm dropping and randomisation outcome are experienced. We will explore if these influence the decision to remain in the study. By evaluating site staff experience of the EXPERTS-ALS platform study, we will identify challenges or barriers to implementation as well as study procedures which work well, in comparison to traditional fixed study designs.

